## **7.0 Demographics, Baseline Characteristics, Medical History, and Prior/Concomitant Medications**

Demographics, baseline characteristics, medical history, prior medication, and concomitant medication will be summarized by previous GnRHa treatment status and overall using the Full Analysis Set. Categorical variables will be summarized with the number and percentage of subjects; percentages will be calculated based on the number of non-missing observations. Continuous variables will be summarized with descriptive statistics (number of non-missing observations, mean and standard deviation, median, minimum, and maximum).

## **7.1 Demographics and Baseline Characteristics**

Continuous demographic variables include age, weight, height, body mass index (BMI), and BMI SD score. Categorical demographic variables include sex, ethnicity, and race.

For CPP history, age at onset of CPP (in years), time between onset of puberty and start of CPP treatment (in years), time since first seen by a physician for CPP to start of CPP treatment (in years) will be summarized by sex and overall.

For family history, target height, mother's age at puberty and height, father's age at puberty and height will be summarized by sex and overall.

For bone age (in years) and height (in cm) related parameters, bone age, BA/CA (ratio of bone age to chronological age), BA-CA (bone age minus chronological age), and growth rate (cm/year) will be summarized by sex and overall.

For diagnostic results for CPP at baseline, brain tumor presence by MRI, brain tumor presence by CT scan, other brain abnormality by MRI, other brain abnormality by CT scan, and adrenal gland abnormality (yes) will be summarized by sex and overall.

In addition, the following baseline disease characteristics will be summarized for female and male:

- For female: tanner staging of breast, tanner staging of pubic hair, menarche status (yes/no), age at first menstruation (in years), bleeding per month (in days), spotting per month (in days), bleeding or spotting per month (in days), uterine length (in cm), uterine/ovary abnormality presence (yes), uterine volume, left ovarian volume, right ovarian volume, endometrial stripe presence (yes), thickness of endometrial stripe (in mm).
- For male: tanner staging of genitalia, tanner staging of pubic hair, left testicular volume, left testicular length, right testicular volume, right testicular length, and testicular abnormality presence (yes).

## **7.2 Medical History**

Medical history will be coded using the Medical Dictionary for Regulatory Activities (MedDRA). The actual version of the MedDRA coding dictionary will be noted in the statistical tables and clinical study report. The number and percentage of subjects in each medical history category (by MedDRA system organ class and preferred term) will be summarized for the FAS. The system organ class (SOC) will be presented in alphabetical order, and the preferred terms will be presented in alphabetical order within each SOC. Subjects reporting more than one condition/diagnosis will be counted only once in each row (SOC or preferred term).

## **7.3 Prior and Concomitant Medications**

Prior and concomitant medications will be summarized by generic drug name using the World Health Organization (WHO) Drug Dictionary.

Prior medications are those medications with a start date prior to the first study drug administration date. Prior medications will be summarized separately for prior CPP medications and other medications.

Concomitant medications during Part 1 are those medications, other than study drug, taken during the Part 1 of Treatment Period with an end date after the first dose of study drug or ongoing at the end of the study, and a start date prior to the last day of study drug for Part 1. Concomitant medications during Part 2 are those medications, other than study drug, taken during the Part 2 of Treatment Period with an end date after the first dose of study drug at Part 2 or ongoing at the end of the study, and a start date prior to the last day of study drug for Part 2.

## **8.0 Efficacy Analyses**

### **8.1 General Considerations**

For all efficacy endpoints, the descriptive statistics will be provided by previous GnRHa treatment status (naïve or previously treated) and combined. The descriptive statistics

include the number of observations, mean, standard deviation, minimum, median, and maximum for continuous variables; and number and percentage for categorical variables.

Subjects with missing GnRHa-stimulated LH test results at a specific scheduled visit will be counted as suppression failures for that visit.

## **8.2 Primary Efficacy Analysis**

The primary efficacy endpoint is the proportion of subjects with suppression of GnRHa-stimulated LH (< 4 mIU/mL) at Week 24, after the first dose of study drug but before the Week 24 dose. The numerator will be the number of subjects with suppression of GnRHa stimulated LH (< 4 mIU/mL) at Week 24, and the denominator will be the number of subjects who received study drug at the Day 1 visit. The proportion of subjects suppressed and the two-sided 95% confidence interval based on the binomial distribution (Clopper-Pearson exact method) will be provided by previous GnRHa treatment status and overall. Peak stimulated LH will be calculated by taking the maximum LH concentrations observed at 30 or 60 min following a GnRHa stimulation test for scheduled assessments.

## **8.3 Secondary Efficacy Analyses**

Unless otherwise specified, categorical data will be summarized by number and percentage; and continuous data will be summarized by sample size, mean, median, standard deviation, minimum, and maximum.

For the proportion of subjects with LH suppression at each scheduled assessment, the numerator will be the number of subjects with suppression of GnRHa stimulated LH (< 4 mIU/mL) at that visit, and the denominator will be the number of subjects who received study drug at the Day 1 visit. The proportion and the two-sided 95% confidence interval based on the binomial distribution (Clopper-Pearson exact method) will be provided by previous GnRHa treatment status and overall.

For the number and percentage of subjects with suppression of basal sex steroids, the two-sided 95% confidence intervals based on the binomial distribution (Clopper-Pearson exact method) will be provided by previous GnRHa treatment status and overall. For the percentage of subjects with suppression of basal sex steroids, if a subject did not receive study drug at the prior scheduled injection visit, the subject will be excluded from the denominator. For example, if Week 24 injection is not done then any assessments after Week 24 the subject will be excluded from the denominator.

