#### **4.9 Missing Data Imputation**

Unless otherwise stated, data will be summarized as observed, i.e., missing data will not be imputed.

For the endpoint of suppression of GnRHa-stimulated LH, subjects who received study drug at the Day 1 visit and are missing GnRHa-stimulated LH results at a scheduled visit in Part 1 will be counted as LH suppression failures for that visit.

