### **5.0 Analysis Populations and Important Subgroups**

#### **5.1 Analysis Population**

The Full Analysis Set (FAS) consists of all subjects who received at least 1 dose of study drug. The FAS will be used for all efficacy and baseline analyses.

The safety Analysis Set consists of all subjects who received at least 1 dose of study drug.

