### **Part 2 of the Treatment Period:**

Last day of study drug for Part 2 – First dose date for Part 2 + 1

In addition, the number and percentage of subjects will be summarized separately for Part 1 and Part 2 for the following categories:

- Number of injections that each subject received (1 or 2)
- Compliance or non-compliance with the dosing scheme. A subject will be considered non-compliant with the dosing scheme if there was a gap larger than 3 days gap between the last day of one injection and the day of the next injection.

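### Sex-steroid suppression omits missing values and, from Week 44, children without the previous planned injection, while LH suppression at the same visits counts every child dosed on Day 1

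*SAP*

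**What the plan says.** **LH suppression.** In SAP 8.3, at each scheduled assessment, "the denominator will be the number of subjects who received study drug at the Day 1 visit". SAP 8.1 adds: "Subjects with missing GnRHa-stimulated LH test results at a specific scheduled visit will be counted as suppression failures for that visit". SAP 4.9 gives the same rule but words it for Part 1 only: "missing GnRHa-stimulated LH results at a scheduled visit in Part 1 will be counted as LH suppression failures for that visit".

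**Basal estradiol and testosterone suppression.** SAP 8.3 states no missing-value rule, so the default in SAP 4.9 governs: "data will be summarized as observed, i.e., missing data will not be imputed". SAP 8.3 then restricts the denominator: "if a subject did not receive study drug at the prior scheduled injection visit, the subject will be excluded from the denominator". Its example is that "if Week 24 injection is not done then any assessments after Week 24 the subject will be excluded from the denominator".

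**Population.** SAP 5.1 defines the FAS as everyone with at least one dose and says: "The FAS will be used for all efficacy and baseline analyses".

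**Injections.** SAP 6.0 tabulates the number of injections separately for Parts 1 and 2, with 1 and 2 as the only categories. Operations Manual 3.19 schedules two injections in Part 1 (Day 1, Week 24). In Part 2 it schedules one every 24 weeks from Week 48 to Week 120.

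**After stopping study drug.** Protocol 5.5 keeps these children in all regular visits. Operations Manual 3.27 leaves their treatment to the investigator, whether or not they stay in the study. Protocol 5.2 prohibits other GnRH agonists, and Protocol 5.4 withdraws a child who needs another drug that would interfere with the evaluation.

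**The concern.** LH and sex-steroid suppression are companion measures of the same effect at the same visits, yet they follow different rules. A difference between the two rates may therefore come from the denominator and not from the drug, and a single-arm trial has no control group in which that would show.

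The exclusion may also be informative. Protocol 5.4 withdraws a child for lack of suppression when LH is at least 4 mIU/mL and puberty has progressed by more than one stage. Such a child leaves the sex-steroid rate through missing values and, after the next planned injection visit, through the injection rule as well. A child who stops study drug but remains in follow-up is removed by the injection rule even when a hormone value exists. Protocol 5.5 collects that value in order to limit missing data.

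Three smaller defects go with this:
- The rule and its example disagree about a child who resumes dosing.
- The planned injection summary cannot describe Part 2.
- No SAP rule covers hormone values obtained on another GnRHa.

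**Working it through.** **Plan's own figure.** The documents give no figure for sex-steroid suppression. The one precision figure (16.7% with 40 children, SAP 4.4) reproduces: the largest distance from x/40 to a Clopper-Pearson 95% limit is 0.1670, at x = 25. It is not affected by this point. All intervals below use the same exact method.

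**When each difference starts.** The missing-value difference applies from the first endpoint visit, Week 12. Every FAS child has had a first dose, so the injection rule first removes someone at Week 44. The governing injection is Week 24 for Weeks 44 and 48. It is Week 48 for Week 72, Week 72 for Week 96, Week 96 for Week 120, and Week 120 for Week 144.

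**Rule against example.** Take a child who misses Week 24 and is dosed at Week 48 and afterwards. Both wordings exclude Weeks 44 and 48. At Weeks 72, 96, 120 and 144 the rule includes the child, because the preceding planned injection was given. The example, read literally, still excludes the child. The denominator thus differs at four visits.

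**Injection categories.** Part 2 has (120 − 48)/24 + 1 = 4 planned injections. The categories stop at 2.

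**Illustration (all counts assumed).** 36 girls dosed on Day 1: 32 on treatment and suppressed, 2 with missing values, 2 stopped but followed without another GnRHa.

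| Analysis | Rate | 95% CI |
|---|---|---|
| Planned table | 32/32 = 100% | 89.1–100 |
| All-dosed, both followed girls suppressed | 34/36 = 94.4% | 81.3–99.3 |
| All-dosed, one suppressed | 33/36 = 91.7% | 77.5–98.2 |
| All-dosed, neither suppressed | 32/36 = 88.9% | 73.9–96.9 |

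The gap is 5.6 to 11.1 points.

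**Sensitivity to the counts.** Again take 36 girls, now with 2 observed as unsuppressed while on treatment. Let k lack the prior injection and m have other missing values, none of them counting as suppressed. The planned rate is (36 − k − m − 2)/(36 − k − m); the all-dosed rate is (36 − k − m − 2)/36.

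| k, m | Planned | All-dosed |
|---|---|---|
| 0, 0 | 34/36 = 94.4% | 34/36 = 94.4% |
| 2, 0 | 32/34 = 94.1% | 32/36 = 88.9% |
| 2, 2 | 30/32 = 93.8% | 30/36 = 83.3% |
| 4, 2 | 28/30 = 93.3% | 28/36 = 77.8% |

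The planned rate barely moves as children leave.

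**Before Week 44.** One missing estradiol value among 36, the rest suppressed: 35/35 = 100% against 35/36 = 97.2%.

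**Boys.** One excluded failure changes 9/10 = 90.0% to 9/9 = 100% with 10 boys, and 3/4 = 75.0% to 3/3 = 100% with 4.

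**LH on another GnRHa.** With 36 of 40 suppressed on study drug the rate is 90.0% (76.3–97.2). If one of the other 4 is followed with LH below 4 mIU/mL on another agent, a literal reading gives 37/40 = 92.5% (79.6–98.4), or 1/40 = 2.5 points per child.

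**The case against.** The best defence is that an on-treatment denominator is a proper, prespecified choice for a maintenance endpoint. Protocol 2.1 foresees that therapy ends when family and practitioner agree that puberty should resume. Previously treated children may enter at up to 10 years (girls) or 11 years (boys), and visits run to Week 144. Planned stops are therefore likely, and an all-dosed table scores those with missing values as failures. This stands, and it is why the all-dosed table should support the on-treatment table and not replace it. SAP 5.1 does not make the exclusion an error either: it names the population, and SAP 8.3 sets a denominator for one endpoint.

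The exclusions are also partly visible. The tables give number and percentage, and SAP 4.3.3 summarises change from Baseline in basal estradiol and testosterone with no injection exclusion stated. Neither display shows whether the excluded children were suppressed or why they were not dosed.

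Four stronger readings are tempting, but the documents do not support them:
- *Missing LH drops out in Part 2 because SAP 4.9 limits the failure rule to Part 1.* With 4 of 40 missing, that would give 36/36. The default in SAP 4.9 yields to specific rules. SAP 8.3 fixes the LH denominator at every assessment and SAP 8.1 has no Part 1 limit, so the result is 36/40 = 90.0%. The mismatch is one of wording.
- *Every child with LH of 4 mIU/mL or more leaves the denominator.* The lack-of-suppression criterion in Protocol 5.4 also requires more than one stage of progression. A child with raised LH alone who is dosed and measured stays in both rates.
- *Values on another GnRHa will commonly inflate LH suppression.* Protocol 5.2 and 5.4 make such values uncommon. What remains is a gap for children followed under Protocol 5.5 and Operations Manual 3.27. For sex steroids it is narrower still, limited to a switch within a dosing interval.
- *The primary result is affected.* The injection rule cannot act before Week 44. The other-GnRHa gap reaches Week 24 only if a child switches within the first dosing interval.

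**Conclusion.** The point holds for secondary, descriptive endpoints, with low to moderate severity. The two rules differ at every visit in how missing values are treated, and from Week 44 also in who is counted. The rule and its example cannot both be programmed for a child who resumes dosing, and the injection categories do not fit Part 2.

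The size cannot be derived from the documents. It is zero if no injection is missed and no value is missing. Under the assumed 36 girls with four off treatment or missing, it is about 6 to 11 points, and each girl moves the all-dosed rate by 1/36 = 2.8 points. The effect per boy is larger if there are few boys.

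The direction is not fixed for children who are followed off drug. Leaving them out raises the rate only if they fail more often than the children kept.

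**What to change.** In the SAP:
1. Keep the on-treatment sex-steroid table, with one stated re-entry rule and an example that agrees with it.
2. Add a supportive table whose denominator is all Day 1 dosed children of the relevant sex. Count missing values as not suppressed, and use values off study drug without another GnRHa as measured.
3. For LH and sex steroids, count values obtained after another GnRHa was started as not suppressed.
4. Extend the Part 2 injection categories to 4. Show missed injections by visit and recorded reason, including planned end of therapy and COVID-19.
5. Remove the Part 1 limit from the missing-LH rule in SAP 4.9, so that it matches SAP 8.1 and 8.3. This changes no number.

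Protocol 5.2 and 5.4 must also be reconciled with Protocol 5.5 and Operations Manual 3.27 on children who start another GnRHa.

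The cost is SAP wording, one table and one display. Concomitant therapy, discontinuation reason and COVID-19 forms are already collected. The downside is that planned stops lower the all-dosed rate: if 6 of 36 girls stop as planned and have no later values, it is 30/36 = 83.3% (67.2–93.6) against 30/30 = 100% (88.4–100) on treatment. For this reason the added table should be labelled supportive and read with the by-reason display.

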#### **8.4 Other Efficacy Analyses**

Unless otherwise specified, categorical data will be summarized by number and percentage; and continuous data will be summarized by sample size, mean, median, standard deviation, minimum, and maximum.

For the number and percentage of subjects who fail suppression of peak stimulated LH per primary endpoint analysis, the 95% confidence intervals will also be provided.

### **9.0 Safety Analyses**

#### **9.1 General Considerations**

The Safety Analysis Set consists of all subjects who received at least 1 dose of study drug. All safety analyses will be performed by previous GnRHa status (naïve or previously treated), and overall.

The following summary statistics will be presented for subjects who have both baseline and post-baseline values for laboratory parameters and vital signs: the mean value at baseline and at each respective protocol specified visit, and the mean, standard deviation and median for changes from Baseline. Categorical data will be summarized using frequencies and percentages.

## **9.2 Analysis of Adverse Events**

### **9.2.1 Treatment-Emergent Adverse Events**

Treatment emergent adverse events are defined as any event with an onset date that is after the first dose of study drug and with an onset date no more than 12 weeks after the end of the effect of study drug (24 weeks after the date of the last administration of study drug). Events where the onset date is the same as the study drug start date are assumed to be treatment emergent.

#### **9.2.1.1 Adverse Event Overview**

The number and percentage of subjects experiencing treatment-emergent adverse events will be summarized for the following AE categories. In addition, the number and percentage of subjects experiencing treatment-emergent adverse events per 100 patient-years will be summarized.

- Any treatment-emergent adverse events
- Any treatment-emergent adverse events related to COVID-19
- Any treatment-emergent adverse events that was rated as related to study drug by the investigator
- Any treatment-emergent severe adverse events
- Any treatment-emergent serious adverse events
- Any treatment-emergent adverse events leading to discontinuation of study drug
- Any treatment-emergent adverse events leading to death
  - Deaths occurring  $\leq$  36 weeks after last dose of study drug
  - Deaths occurring  $>$  36 weeks after last dose of study drug
- Any treatment-emergent adverse event of special interest

### **9.2.1.2 Adverse Events by System Organ Class and Preferred Term**

The number and percentage of subjects experiencing treatment-emergent adverse events will be tabulated using primary Medical Dictionary for Regulatory Activities (MedDRA) by System Organ Class (SOC) and Preferred Term (PT). Subjects reporting more than one adverse event for a given PT will be counted only once for that term (most severe incident for the severity tables and most related incident for the relationship tables). Subjects reporting more than one type of adverse event within a SOC will be counted only once for that SOC. Subjects reporting more than one type of adverse event will be counted only once in the overall total.

### **9.2.1.3 Adverse Events by Preferred Term**

The number and percentage of subjects experiencing treatment-emergent adverse events will be tabulated by Preferred Term (PT) by decreasing frequency of overall.

### **9.2.1.4 Adverse Events by Maximum Relationship**

Treatment emergent adverse events will be summarized by maximum relationship to study, as assessed by the investigator. If a subject has an adverse event with unknown relationship, then the subject will be counted in the relationship category of "unknown," even if the subject has another occurrence of the same event with a relationship present. The only exception is if the subject has another occurrence of the same adverse event with a relationship assessment of "Reasonable Possibility." In this case, the subject will be counted under the "Reasonable Possibility" category.

### **9.2.1.5 Adverse Events by Maximum Severity**

Treatment-emergent adverse events will be summarized by maximum severity. If a subject has an adverse event with unknown severity, then the subject will be counted in the severity category of "unknown," even if the subject has another occurrence of the same event with a severity present. The only exception is if the subject has another occurrence of the same adverse event with the most extreme severity – "Severe." In this case, the subject will be counted under the "Severe" category.

### **9.2.1.6 Adverse Events of Special Interest**

Adverse events of special interest will be summarized by SOC and PT and will be based on standardized or company MedDRA queries (SMQs or CMQs), or based on adjudication results.

The following Adverse Events of Special Interest (AESI) will be summarized:

- Bone fracture
- Slipped capital femoral epiphysis
- Neuropsychiatric events
- Seizure/convulsion
- Injection site reaction
- Hypersensitivity reactions

Detailed information about the search criteria is provided in [Appendix A](#).

### **9.2.1.7 Hormonal Flare Response Adverse Events**

The number and percentage of subjects with hormonal flare response adverse events will be summarized by SOC and PT.

Data on acute-on-chronic symptoms collected from phone calls and visits after study drug injections will be summarized with number and percentage for who reported abnormal behavior, abnormal physical symptoms or any abnormalities.

A blood sample will be collected 48 hours after the second injection (Week 24) of LA 45 mg 6-month, which will be used to assess the biochemical AOC phenomenon by measuring LH and estradiol (female subjects) or testosterone (male subjects) in all subjects (both pre-treated and naïve). The AOC biochemical definition is LH > 4 mIU/mL and estradiol > 20 pg/mL or testosterone > 30 ng/dL 48 hours after the second injection of leuprolide acetate at the Week 24 visit. The number and percentage of subjects with biochemical AOC phenomenon will be provided.

